Title: Activated Macrophages and Ozone Toxicity

Principal Investigator: [name], MPH

Funding Source: National Institutes of Health

1. Purpose/Specific Aims

The purpose of the study is to better understand the mechanisms of lung injury from ozone exposure. Ozone is a ubiquitous urban air pollutant that causes adverse health effects in both healthy and susceptible individuals. The study will focus on the inflammatory mechanisms which follow ozone exposure. Specifically, the study will determine the role of different types of macrophages, proinflammatory M1 macrophages and anti-inflammatory reparative M2 macrophages, in lung injury.

The study will incorporate a pilot study to refine protocols and measure novel soluble inflammatory markers in sputum supernatant including cytokine, chemokines, eicosanoids and prostaglandins following ozone exposure. Samples from the pilot will be used to identify which markers will be measured in the main study.

1.1 Objectives

1. The phenotype of macrophages responding to ozone exposure will be assessed (main study).
2. The objective of the pilot study is to pilot the study protocols. Additionally, the response of novel inflammatory markers to ozone exposure will be assessed.
3. The response of the respiratory microbiome to ozone exposure will be assessed.

1.2 Hypotheses

The hypothesis for the main study is that ozone toxicity is a result of cytotoxic proinflammatory macrophages overwhelming the activity of anti-inflammatory reparative macrophages.

2. Background and Significance

Ozone is a ubiquitous air pollutant and the main component of photochemical smog. It remains one of the most problematic air pollutants to control because it is formed from intermediates that arise from multiple sources [1-3]. Inhaled ozone has been shown to irritate and damage the lung in both healthy and susceptible individuals, including children and the elderly [3, 4]. Ozone causes inflammation and constriction of the airways, reducing pulmonary function. Ozone also exacerbates asthma and suppresses nonspecific immunity increasing the susceptibility of exposed individuals to respiratory infections [5, 6]. Epidemiologic studies in the U.S. have demonstrated that for every 10 ppb increase in peak ozone levels, the total death rate for the same day increases by 0.41% [4], while a more recent US/European study estimated 0.56% [7]. Adverse effects of ozone are even greater in the developing world where ozone levels can be significantly higher than in the U.S. with a concomitantly greater health burden. In this regard, despite control attempts and much lower standards, daily maximum ozone concentrations have recently reached 128 ppb in Shanghai and 225 ppb in Mexico City [8, 9].

Thus, new strategies to reduce lung injury from ozone and other air pollutants by elucidating specific pro- and anti-inflammatory mechanisms that contribute to ozone toxicity are key to public health.

Accumulating evidence suggests that tissue injury induced by ozone is due, not only to direct effects of ozone on the lung, but also indirectly to the actions of resident and infiltrating macrophages [10-12]. These cells are activated to release a myriad of inflammatory mediators that fight infection, protect against xenobiotics, activate adaptive immunity, and promote wound healing. These diverse activities of macrophages are thought to be mediated by distinct subpopulations that develop in response to inflammatory signals within their microenvironment. Two major subpopulations have been identified: classically activated M1 macrophages which release cytotoxic/proinflammatory mediators and alternatively activated M2 macrophages, which release mediators that suppress inflammation and initiate wound repair [13, 14].

Our overall goal is to analyze the distinct contributions of M1 and M2 macrophage subpopulations to ozone-induced lung injury. Preliminary data demonstrate that both macrophage populations play a role in ozone toxicity. Whereas initially, classically activated M1 macrophages contribute to lung injury by releasing cytotoxic/proinflammatory mediators, subsequent release of anti-inflammatory and mitogenic mediators by M2 macrophages promotes tissue repair. We hypothesize that ozone-induced injury and altered lung mechanics ensue when M1 macrophage proinflammatory/cytotoxic activity predominates over the antiinflammatory/reparative functions of M2 macrophages. To test this hypothesis, the phenotype of macrophages responding to ozone-induced injury will be analyzed in animals and humans. Additionally, mice with specific defects in M1 or M2 macrophages, or monocyte precursors, will be used to assess their contribution to toxicity. Lineage tracking strategies will be used to analyze the origin of macrophage subpopulations in the lung and mechanisms mediating their accumulation.

The hypothesis that inhaled ozone causes a sequential accumulation of M1 and M2 macrophages in humans and animals has not been previously tested. Findings that results in humans are comparable to mice would provide strong support for the relevance of our mouse models to human toxicity resulting from ozone exposure. For translational human studies, we will use induced sputum as a source of macrophages [15-17]. The advantage of induced sputum is that it is a safe and non-invasive technique; additionally, induced sputum selectively samples the surfaces of the large conducting airways, a primary target for ozone effects in humans [15, 18].

The supernatant from the induced sputum samples will be analyzed for markers of inflammation, including chemokines, cytokines, prostaglandins and eicosanoids. Eicosanoids, including 20-HETE and 15-HETE, have been shown to induce airway hyper-responsiveness and to be increased by oxidant exposure in animals [19]. In addition to directly inducing inflammation, oxidants, such as ozone, can generate free radicals altering the oxidant/antioxidant balance within the respiratory tract. The release of ROS leads to transcription of pro-inflammatory cytokine and chemokine genes, increased release of pro-inflammatory mediators and up-regulation of adhesion molecules [20, 21]. Mononuclear cells

isolated from induced sputum in subjects with asthma express IL-4 and IL-10 levels to a greater degree than cells from healthy controls, suggesting an enhanced immunologically mediated inflammatory response [22]. Exhaled breath condensate samples, blood samples and urine samples will also be analyzed for markers of inflammation.

The characterization of the lung microbiome is currently the focus of an ongoing study at Rutgers (Pro20140000953). The study compares microbial communities in numerous samples from the respiratory tract (including lung cells collected by bronchoalveolar lavage, induced sputum, oral wash, and oropharyngeal samples). Environmental exposures may alter the lung microbiome, affecting disease progression [23-25]. Samples will be collected by all of the above methods except bronchoalveolar wash to determine the response of the microbiome to ozone exposure.

The current USEPA standard for ozone is 0.070 ppm averaged over an 8 hour day. This is meant to protect not only healthy individuals, but those more sensitive to ozone's effects such as infants, children, those with asthma, and those with other chronic lung conditions such as COPD. The proposed exposure concentration of ozone (0.2 ppm, 3 hours) is almost twice maximal levels reported in the world's most polluted cities (i.e., Mexico City); however, this concentration and higher concentrations (up to 0.4 ppm, 2 hours) with exercise have been used extensively for mechanistic studies at United States Environmental Protection Agency (USEPA), the University of Southern California (USC), the University of California, San Francisco (UCSF), the University of California, Davis (UC Davis), the University of Rochester, and other institutions for over 40 years with no adverse effects in hundreds of subjects, including asthmatics, beyond transient and expected physiologic declines in spirometry, reported [26-34]. For instance, one recent study at University of Rochester exposed healthy exercising subjects to 0.2 ppm of ozone for 3 hour, identical to our proposed protocol [27]. 7-10% declines in FEV1 were observed 0.5 hours after exposure had largely resolved by 4 hours following exposure. Another study using the roughly equivalent 0.3 ppm ozone for 2 hours with exercise showed transient FEV1 declines of 7-15% [26]. Our exposures will be limited to 3 hours and will only occur once. Based on published studies, subjects are not expected to experience more than transitory effects including symptoms of mucosal irritation, cough or headache, but these are expected to be mild and dissipate within an hour after the exposure is terminated.

3. Research Design and Methods

The study is a single blind randomized cross-over design. Subjects (up to 68 healthy men and women) will participate in the study (48 non-smokers and 10 smokers in the main study and 5-10 in the pilot study). Eligible subjects will have 5 clinic visits: one screening visit, 2 exposure visits, and 2 post-exposure sample collection visits. Each subject will participate in 2 exposure sessions, one to clean air (ozone<5ppb) and one to 0.2 ppm ozone in the Controlled Exposure Facility (CEF) at the Environmental and Occupational Health Sciences Institute (EOHSI). The order of the exposure sessions will be randomized. Up to 2 subjects may participate in each exposure session. Induced sputum samples will be collected at the baseline (during screening) then at one of three pre-selected time periods (24, 48 or 72 hours) following each exposure session. Breath, blood, oral washes, oropharyngeal swabs, and urine samples will be collected at each visit.

Subjects will undergo telephone screening. If eligible they will be scheduled for the screening visit. Subjects will be asked to refrain from antioxidants, over the counter anti-inflammatory medications, strenuous exercise, alcohol, home air purifiers, unvented household combustion sources, gases and fumes for 48 h prior to the screening visit and before each exposure visit through the post-sample collection period. Non-smokers will also be asked to avoid tobacco smoke.

Subjects will be consented then scheduled for a screening visit to determine eligibility. Subjects will be asked to refrain from eating for 2 hours prior to the screening visit. On the day prior to the screening visit, subjects will be called/mailed/texted to confirm their appointment. If the subject reports a respiratory or other acute illness, including active allergies, during the four prior weeks or if they have taken any medication for allergies or respiratory illness, their visit will be rescheduled to a later date. The screening visit will include a complete medical history and physical examination (including height, weight, and three blood pressure measurements), lab tests (CBC with differential and platelet count, urinalysis, and standard metabolic screen), spirometry, impulse oscillometry (IOS), and ECG. A pregnancy test (urine hCG) will be administered to females at enrollment and before each exposure session. Exhaled breath condensate (EBC) samples will also be collected using an RTube™ (the condensate collection system manufactured by Respiratory Research, Inc.) or using the Jaeger EcoScreen. With the RTube™, each subject uses a new and separately packaged device to eliminate any risk of infection transmission. The samples are collected by having patients breathe through a one-way valve into a cooled condenser for 5 to 15 minutes. As much as 1 ml of condensed liquid can be collected in a 5-minute period. There is virtually no risk and no spuriously induced inflammation in the lung from this procedure, and it may be serially repeated [35]. Subjects will be asked for permission to store excess EBC sample for future use by the study investigators.

Figure 1. R-tube (left); Ecoscreen (right)

Impulse oscillometry (IOS) is an additional noninvasive and effort-independent technique to measure airway resistance and capacitance. The airway resistance and capacitance, reflecting airway compressibility, is measured at normal tidal breathing. This physiologic technique also allows measurement of peripheral and central airway resistance. IOS waves are measured for 30 seconds of tidal breathing and the maneuver is repeated three times. This technique has no known side effects and is a safe test providing a great deal of information regarding peripheral airway resistance.

Oral washes and oropharyngeal swabs will be collected for microbiome analyses. For the oral wash (OW), participants will gargle with 10 ml sterile 0.9% saline and expel the sample into a specimen container. Oropharyngeal swabs (OS) will be collected using a new, sterile cotton

swab. While wearing gloves and depressing the tongue with a sterile tongue depressor, the swab will be inserted into the back of the oral cavity. The participant will be asked to say "aahh" to elevate the uvula and with a sweeping motion the posterior pharyngeal wall and tonsilar pillars will be swabbed. By applying a little force a large quantities of mucosa will be collected. Care will be exercised to avoid swabbing the soft palate or touching the tongue with the swab tip. The swab will immediately placed in a sterile tube and stored with the other samples for transport.

In addition to the EBC, oral washes, and oropharyngeal swab samples, urine and blood (approximately 10 ml) samples will be collected at the screening visit. The urine samples will be analyzed for eicosanoids and other markers of inflammation. The urine samples of the smokers will also be analyzed for cotinine to confirm their smoking status. The blood samples will be processed by [name] lab at EOHSI. Plasma from the blood samples will be stored in the principal investigator's private freezer for future analysis of markers of ozone response; no genetic analyses will be performed on these stored samples. Only study investigators will have access to these samples.

At screening, subjects will be asked to provide an induced sputum specimen (baseline sample), which will be immediately analyzed for the presence of plugs. Using the method described by Pin et al. [36] and Alexis et al., [37] subjects inhale increasing concentrations of saline (3%, 4% and 5%) for 3 consecutive 7-minute periods through a mouthpiece without a valve. To reduce the risk of bronchospasm, following the recommendations of the European Respiratory Commission [38], albuterol (180 mcg; 2 puffs of a standard metered inhaler) will be given to subjects 15 minutes prior to the start of the induction. Post-dose spirometry is performed to obtain a baseline FEV-1. The subject will be asked to breathe through his/her mouth during the induction. If the subject is observed to breathe through his/her nose, he/she will be asked to monitor his/her breathing and will be offered a nose clip to use during the induction. After each period of inhalation, an FEV-1 is measured for safety. If the FEV-1 decreases by 20% or more from the post-dose FEV-1, the procedure is stopped. After rinsing the mouth, swallowing water and blowing the nose to minimize contamination by saliva or post nasal drip, subjects will cough sputum into a sterile container. Subjects unable to provide an adequate specimen (70-75 mg of plugs) will be excused from the study. In the main study, subjects will be assigned to a post-exposure sample collection time (24, 48, or 72 hours) to be used for both exposure sessions. In the pilot study and for all smokers, all subjects will be assigned to the 24 hour post-exposure sample collection. The exposure sessions will be scheduled.

Subjects may be screened (telephone and screening visits) year-round. For the main study, the exposure visits will be scheduled between October and June, consistent with low ambient ozone months in New Jersey. For the pilot study, since only acute responses are examined (24 hours of the exposure), the screening and exposure visits will take place year-round. If over six months have passed between the screening visit and scheduling the exposures, those subjects will be re-consented and the screening visit will be repeated.

Each exposure session will be 3 hours in duration. Subjects will be called the day prior to the visit to confirm the appointment. If unable to be reached by phone, reminder texts or emails may be sent from a Rutgers-authenticated computer. Subjects will be asked to report any

current or recent respiratory symptoms. If subjects report any symptoms within the previous 4 weeks, the visit will be rescheduled. Subjects will be asked to refrain from eating for 2 hours prior to the exposure visit. At the start of the visit, the subject's blood pressure, pulse, and temperature will be measured. IOS and spirometry will be performed before and after the exposure session. Two questionnaires will also be administered before the exposure session: a stress questionnaire and a symptom questionnaire. If the subject reports the presence of any respiratory symptoms, the exposure session will be canceled. During the exposure, heart rate will be measured using a wireless monitor (H7; Polar USA). Subjects will be asked to alternate (every 15 minutes) rest and mild/moderate exercise periods on a cycle ergometer to maintain an average heart rate of approximately 60% maximum heart rate (220-age). The exercise is necessary as healthy human subjects are relatively insensitive to ozone [39, 40]. The exercise schedule may be modified to maintain the ventilation rate or for the subject's comfort. After the exposure session, the stress and symptom questionnaires will be administered. An exposure type questionnaire will also be administered immediately after the exposure. If the subject reports any physical symptoms or has a 20% decrease in his/her FEV1 after the exposure session, the study physician will be consulted. Subjects will be given verbal and written instructions to contact the Robert Wood Johnson Medical School Pulmonary Division if they experience any breathing problems after leaving EOHSI. Subjects will inform the responding pulmonologist that he/she is a study subject. As an additional precaution, subjects will be given a rescue inhaler to use only if directed to do so by the responding pulmonologist. Subjects will be shown how to use the inhaler prior to leaving the EOHSI clinic. The pulmonologist will inform [name] of any calls made to the pulmonologist and any treatment. The symptom questionnaire will be administered to each subject the day after exposure. For subjects returning at 24 hours for the post-exposure sputum sample, the questionnaire will be administered in person. For all other subjects the questionnaire will be administered by phone. As a secondary check, the questionnaire will ask the study subject if he/she contacted the Pulmonary Division. If the subject reports the presence of any symptoms or called the Pulmonary Division, the study physician will be consulted, prior to the collection of any samples.

Immediately before and after each exposure session EBC samples will be collected using the same methods as in the screening visits. In addition to the EBC samples, urine, oral washes, oropharyngeal swabs, and blood samples will be collected before and after each exposure session. During the second exposure visits, an additional blood sample will be collected for genotyping of GST polymorphisms. The urine samples will be analyzed for eicosanoids and other markers of inflammation. The blood samples will be processed by either [name] lab (research blood for future use) or the Rutgers University Cell and DNA Repository facility core at EOHSI (sample for genetic analysis).

Subjects will be asked to return for a follow-up visit either 1, 2, or 3 days after each exposure visit. Subjects will be asked to refrain from eating for 2 hours prior to the visit. The blood pressure, pulse rate, and oral temperature will be checked. IOS and spirometry will be performed and an induced sputum sample will be collected. The symptom and stress questionnaire will be administered. The blood, urine, oral washes, oropharyngeal swabs, and EBC samples will also be collected.

Sputum samples obtained after the ozone exposure may be compared with samples collected either at the screening visit or after the clean air exposure. If the subject is randomized to ozone exposure first and is unable to produce a sputum sample after the ozone exposure, the subject will be withdrawn from the study.

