3.3 Sample Size Justification

Calculations are based on published human exposure studies [41, 42] demonstrating 2.3-fold and 1.6-fold increases (SE=8%) in mean fluorescence intensity of sputum leukocyte expression of markers of M1 (CD14) and M2 (CD16) macrophages following ozone exposure at 24 h compared to clean air. The SDs for changes [the square root of $2(1-\rho)\text{SD}^2$] were calculated where rho is the intra-person correlation (0.5) between measurements. Based on this, 16 subjects/exposure group are needed to achieve 90% power using 0.05 level two-group t-tests.

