3.4 Subject Selection

Two subject populations will be studied: smokers (n=10) and non-smokers (n=70). The pilot study will recruit up to 10 people (non-smokers) and the main study will recruit 70 people (10 smokers & 60 nonsmokers).

3.4.1 Inclusion Criteria – both smokers and non-smokers.

Healthy men and women (n= up to 80) between the ages of 18 and 40 will be recruited for the study. Subjects who participate in the pilot study will also be eligible to participate in the main study.

Subjects must have been fully vaccinated for COVID-19 – people are considered fully vaccinated for COVID-19 ≥ 2 weeks after they have received the second dose in a 2-dose series (e.g., Pfizer-BioNTech or Moderna), or ≥ 2 weeks after they have received a single-dose vaccine (e.g., Johnson and Johnson).

Additional Inclusion Criteria for Smokers: currently smoking at least one cigarette each day.

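### Collection time has no stated random mechanism, order is not stated to be stratified within time groups, and the primary paired tests have no period term

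*Protocol*

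**What the plan says.** **Order.** Protocol section 3: "The order of the exposure sessions will be randomized". It gives no ratio, blocking or stratification factor.

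**Collection time.** The same section says that sputum is taken "at one of three pre-selected time periods (24, 48 or 72 hours) following each exposure session" and, for main-study participants, that "subjects will be assigned to a post-exposure sample collection time (24, 48, or 72 hours) to be used for both exposure sessions". It does not say how the time is chosen. One non-random rule is explicit: "In the pilot study and for all smokers, all subjects will be assigned to the 24 hour post-exposure sample collection".

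**Time course.** Protocol section 2 calls it an untested hypothesis that "inhaled ozone causes a sequential accumulation of M1 and M2 macrophages" in humans and animals. The main-study hypothesis in section 1.2 concerns proinflammatory activity overwhelming reparative activity and names no time sequence.

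**Group size.** Section 3 plans "48 non-smokers and 10 smokers in the main study and 5-10 in the pilot study". Section 3.4 says "the main study will recruit 70 people (10 smokers & 60 nonsmokers". Section 3.3 states: "Based on this, 16 subjects/exposure group are needed to achieve 90% power using 0.05 level two-group t-tests".

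**Analysis.** The SAP lists three primary outcomes, at 24, 48 and 72 h. Each is a paired t-test of the M2 to M1 ratio at the 0.05 level. Protocol section 7 describes ANCOVA with baseline as covariate. Neither includes a period or sequence term, and no interval between the two exposures is given.

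**Withdrawals worded for one order only.** Section 3 withdraws a subject who has ozone first and gives no sputum afterwards. Section 4.4 stops a subject who has bronchospasm with clean air before having had ozone.

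**The concern.** Two separate things are at stake.

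The first is the time course. Each subject gives post-exposure sputum at one delay only, so any statement that M1 cells come first and M2 cells follow compares different people. Without random assignment of the delay, a difference between 24 and 72 h may reflect who was in each group. Section 8 confines procedures to working hours. On a Monday-to-Friday week (assumed), a Thursday exposure fits only a 24 h return and a Friday exposure only a 72 h return, so scheduling could steer subjects into groups.

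The second is the precision of each primary test. Randomising order protects the ozone versus clean-air contrast against period effects on average. Here each time group is analysed alone and is small. If order happens to be uneven in a group, the paired t-test carries part of any shift between the first and second session into the ozone estimate.

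**Working it through.** **1. The plan's own figure.** Section 3.3 arrives at 16. It cannot be reproduced or refuted, because turning a standard error of 8% into a standard deviation needs the source studies' sample size, which is not given. What does check is 48/3 = 16 non-smokers per time group; with 60 non-smokers it is 60/3 = 20. At n = 16, 90% power (two-sided 0.05) needs a standardised effect of 0.87 for a paired t-test and 1.18 for a two-group test.

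**2. Chance of an uneven split.** Assume simple randomisation; the documents name no method. The number taking ozone first is then Binomial(n, 0.5).

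- n = 16, 11:5 or worse: 2 × P(X ≤ 5) = 2 × 6885/65536 = 0.210. At least one of three groups: 1 − (1 − 0.210)³ = 0.507.
- n = 16, 12:4 or worse: 2 × 2517/65536 = 0.077.
- n = 16, exactly 8:8: 0.196. The mean of |n1 − n2|/n is 0.20.
- n = 20, 14:6 or worse (a relative imbalance of at least 40%): 2 × 60460/1048576 = 0.115. At least one of three: 1 − (1 − 0.115)³ = 0.31. The mean relative imbalance is 0.18.

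**3. What an uneven split does.** Let π be the shift from period 1 to period 2, in SDs of the paired difference, n1 the number taking ozone second and n2 the number taking it first. The expected bias of the mean paired difference is π(n1 − n2)/n. At 11:5 this is π × 6/16 = 0.375π; at 12:4 it is π × 8/16 = 0.50π.

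The documents give no value for π, so 0.25, 0.5 and 1 are assumed. Simulation at n = 16 (200,000 runs) gave:

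| Split | Bias in SD (π = 0.25 / 0.5 / 1) | Type I error, paired t-test | Power with period term (effect 0.87 SD) |
|---|---|---|---|
| 8:8 | 0 / 0 / 0 | 0.044 / 0.029 / 0.006 | 0.90 |
| 10:6 | 0.06 / 0.13 / 0.25 | 0.050 / 0.048 / 0.037 | 0.88 |
| 11:5 | 0.09 / 0.19 / 0.38 | 0.057 / 0.075 / 0.10 | 0.85 |
| 12:4 | 0.13 / 0.25 / 0.50 | 0.070 / 0.117 / 0.228 | 0.80 |

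The period-adjusted estimate averages the two sequence-specific mean differences. Its bias is 0 and its type I error is 0.049 to 0.050 at every split.

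**4. Averaged over simple randomisation.** Type I error of the paired test is 0.050, 0.051 and 0.052 for the three values of π, so there is no overall inflation.

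**5. Blocking alone.** At π = 1, the SD of the estimate is √((1 + 1)/16) = 0.35 under simple randomisation and √(1/16) = 0.25 with 8:8 blocks. Power of the paired test rises only from 0.62 to 0.66, because the period shift still sits in its error variance. A period term brings power to about 0.90.

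**6. Withdrawals.** A balanced list does not guarantee balanced completers. The bronchospasm rule is directly asymmetric: the same event with clean air ends participation if air comes first, but not if ozone has already been given. The sputum rule is weaker in effect, because an air-first subject without post-ozone sputum yields no ozone–air pair either. It unbalances the pairs only if failure depends on which session it is.

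**The case against.** The strongest reply is that the SAP tests nothing across times. All three primary tests compare a subject with himself or herself at a fixed delay, so selection into a time group cannot bias them. The sequential hypothesis appears in the background section and has no planned test. This stands, and it confines the selection problem to how the three results are read together.

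A reader might infer that order is unbalanced within time groups. The documents do not say so: they say order is randomised, and blocking may have been used without being described. A reader might also infer that time was assigned by availability. The word used does not exclude random assignment. Section 3 mentions scheduling after assignment, and Monday or Tuesday exposures would allow all three delays. Nor is there evidence that the groups differ by season; all main-study exposures share the October to June window.

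A third tempting reading is that period effects inflate the primary tests' type I error. Averaged over randomised order they do not; the exposure is conditional on the split obtained. The documents report no period effect, which may be zero, and 11:5 is a tail split rather than a typical one.

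What remains is that the assignment method is unstated, that stratification of order is unstated, and that neither analysis would correct an uneven split if one occurred.

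**Conclusion.** The point holds in a limited form. The ozone versus clean-air contrast at each time is sound with respect to selection. The sequence across 24, 48 and 72 h is not protected, because it compares different people and no random mechanism is stated. The explicit rule sending smokers and pilot subjects to 24 h adds a difference by design if they are pooled into that test, which the SAP does not settle.

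For the primary tests the risk is conditional bias and lost precision. At 16 per group under simple randomisation, the chance of 11:5 or worse is 21% for one group and 51% for at least one of three, with 37.5% of any period effect then retained. At 20 per group the risk is smaller but present. These figures rest on simple randomisation, groups of fixed size and no carryover. The bias in SD units also rests on the assumed period shift of 0.25 to 1 SD.

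**What to change.** **If enrolment is still open.** Randomise main-study non-smokers jointly to collection time (1:1:1) and order (1:1), in blocks within time group, so that a group of 16 has 8 in each order. Randomise the smokers' order in a separate block. Add a period term to each primary ozone versus clean-air comparison. The term is needed even with blocking, because blocking removes the bias but leaves the paired test conservative, and withdrawals can still unbalance completers.

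**If enrolment is complete**, as the SAP's past tense suggests it may be: add the period term, state how collection time was assigned, and report the realised order split among completers in each time group. If time was not randomly assigned, limit conclusions to the three within-subject contrasts and make no claim about sequence.

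**Cost.** A revised allocation list, a protocol sentence and a SAP sentence; slightly less freedom in scheduling return visits; and one degree of freedom per test (15 to 14 at n = 16), which leaves power at about 0.90 when order is balanced.
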